16.14. Administration of assessments

- PGI-I (Patient Global Impressions Improvement Scale). The subject and not the examiner (site staff) should make the ratings, but the examiner should be available to clarify any misunderstandings the subject may have about the questions. The examiner should mark the subject's answers on the form.
- CGI-I (Clinical Global Impressions Improvement Scale). The CGI-I is completed by the Investigator after reviewing the subject's PGI-I response and conducting a short interview with the subject regarding their RLS symptoms over the past week compared to baseline. The Investigator will not be permitted access to the subject's IRLS responses.

- **Refractory categorization.** The refractory categorization form should be completed by the Investigator, within 72 hours of EVAL 1.
- IRLS. The subject and not the examiner (site staff) should make the ratings, but the examiner should be available to clarify any misunderstandings the subject may have about the questions. The examiner should mark the subject's answers on the form.
- **MOS-Sleep.** The subject and not the examiner (site staff) should make the ratings, but the examiner should be available to clarify any misunderstandings the subject may have about the questions. The examiner should mark the subject's answers on the form.
- Blinding assessment. The subject and not the examiner (site staff) should make the ratings, but the examiner should be available to clarify any misunderstandings the subject may have about the questions. The examiner should mark the subject's answers on the form.
- The **Daily Questionnaire** will be completed by the subject.
- **Subject characterization** will be completed by the examiner (site staff) based on information from the subject.
- **Medical history** will be completed by the examiner (site staff) based on information from the subject.
- For the **Weekly questionnaire**, the subject and not the examiner (site staff) should make the ratings, but the examiner should be available to administer the questions and clarify any misunderstandings the subject may have about the questions. The examiner should mark the subject's answers on the form.

16.15. Study Exit

Study exit will occur at the conclusion of Eval #11. At study exit, the Investigator/coordinator will complete the study exit eCRF. Adverse events unresolved at study exit will be followed by the Investigator until resolution occurs or at least 60 days after the subject's participation in the study is complete.

16.16. Subject Discontinuation

A subject may be removed from the study prior to completion for any of the following reasons:

• Voluntary withdrawal of consent

- Adverse event preventing further study participation •
- Investigator believes risk of further subject participation outweighs benefit
- Persistent non-compliance or lost to follow-up
- Pregnancy
- Subject no longer meets inclusion criteria •
- Subject makes a significant change to dosage of medications known to interfere with sleep or • RLS symptoms, including sleep medications, antidepressants, sedative antihistamines.

The Investigator or research staff will complete a study exit form in the eCRF for any subject who prematurely discontinues from the study. If discontinuation was the result of an AE, the AE will also be recorded in the eCRF.

Upon discontinuation, subjects will receive partial compensation commensurate with their completed Phases.

16.17. **Study Termination**

The Sponsor may terminate the study as a whole or at individual study sites under the following circumstances:

- Suspicion of risk to subjects, including occurrence of high rate of known AEs or unexpectedly high rate of unexpected AEs
- Poor site compliance with the study protocol ٠
- Inadequate site enrollment •
- Obtaining new scientific knowledge that shows that the study is no longer valid or necessary •
- Persistent non-compliance with IRB or regulatory requirements ٠
- Persistent failure to comply with obligations arising from the clinical trial agreement •
- Other business reasons (e.g., insolvencies or business entity liquidation) •

The sponsor will document reasons for study suspension and notify relevant site Investigators and governing IRBs. If suspension occurred because of a safety issue, all Investigators will be notified. When terminating the study, the sponsor and Investigator will assure that adequate consideration is given to the protection of the subjects' interests.

CONFIDENTIAL

17. Study Endpoints

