7.1. Inclusion criteria (IC)

All subjects are required to meet the following inclusion criteria in order to be considered eligible for participation in this study:

- 1. Subject has received a medical diagnosis of primary restless legs syndrome (RLS).
- 2. Subject is refractory to RLS medication (as defined in section 7.3).
- 3. Subject has moderate-severe RLS symptoms as defined by a score of 15 or greater points on IRLS (International Restless Legs Syndrome Study Group Rating Scale [12]) over the week prior to study entry.
- 4. Subject has RLS symptoms 2 or more nights per week during the week prior to study entry as defined by a score of 2, 3, or 4 on IRLS question #7.
- 5. RLS symptoms are most significant in the subject's lower legs and/or feet.
- 6. RLS symptoms are most significant at bedtime, after bedtime, and/or in the 2 hours before bedtime.

CONFIDENTIAL

- 7. RLS symptoms between 10am and 6pm are not severe.
- Subject agrees to not change dosage or schedule of any medications that are known to impact RLS symptoms during the study, including RLS medications, antidepressants, sleep medications, or sedative antihistamines.
- 9. Subject agrees to not make major lifestyle changes during the study that would significantly affect bedtime, such as major changes to diet, exercise, or career.
- 10. Subject possesses the necessary equipment, internet/phone accessibility, and communication ability to complete electronic questionnaires and respond to electronic communications and phone calls from the research staff throughout the in-home portion of the study.
- 11. Subject is \geq 22 and \leq 79 years of age when written informed consent is obtained.
- 12. Subject has signed a valid, IRB-approved informed consent form, can understand the requirements of the study and instructions for device usage, and can converse in English

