### 6.0 ANALYSIS POPULATIONS

### 6.1 Intent-to-Treat (ITT) Population

The Intent-to-Treat (ITT) Population will include all eligible subjects who pass screening and are randomized into the study.\* The ITT Population Set will be used for the primary analysis of all efficacy endpoints, and subjects will be analyzed based on the treatment to which they are randomized.

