### 6.2 Per Protocol (PP) Population

The Per Protocol (PP) population will include all subjects who pass screening, are randomized into the study, undergo the assigned treatment, and have complete and evaluable Day 28 data, except that:

- (i) Subjects will be excluded from the Per Protocol Population if one or more of the following occurs during or before the Phase of the study corresponding to the endpoint:
  - 1. Dropout or removal from the study.
  - 2. Incomplete or missing data for the endpoint.
  - 3. Clinically significant change in dose or schedule of one of the following classes of medication during the study: RLS medications, antidepressants, sleep medications, or sedative antihistamines.
  - 4. New medical information available after randomization indicates an exclusion criterion.
  - 5. Other protocol deviation occurs that is deemed clinically significant by the investigator.
- (ii) Subjects will also be excluded from the Per Protocol Population if one or more of the following occurs during the Phase of the study corresponding to the endpoint:
  - 6. Device usage on fewer than two-thirds of the nights with RLS symptoms as reported by the subject on the Daily Questionnaire assessments.
  - 7. Missing two or more follow-ups during the Phase (Note: Follow-ups completed out-of-window are not considered "missing")
  - 8. Zero total device uses during the Phase.

The PP Population will be used for a secondary analysis of all efficacy endpoints.

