### 8.2 Key Secondary Efficacy Endpoints Analyses

The key secondary efficacy endpoints below will be analyzed using a fixed sequential method in the order they are listed. Secondary efficacy endpoint #1 will only be analyzed if the primary efficacy endpoint analysis results in rejection of the null hypothesis, and subsequent secondary efficacy endpoints will only be analyzed if all prior secondary efficacy endpoint analyses resulted in rejection of the null hypothesis (e.g., secondary efficacy endpoint #3 would only be tested if the primary analyses of the primary and first two secondary efficacy endpoints result in rejection of the null hypothesis). Analyses of subsequent secondary endpoints will continue hierarchically until the first analysis that results in failure to reject the null hypothesis, and some or all of the secondary efficacy endpoint analyses may not be formally performed.

The key secondary efficacy endpoints are as follows:

- 1. PGI-I response (defined as for CGI-I) at Week 4 of Phase 1 relative to Baseline.
- 2. Reduction in IRLS score at Week 4 of Phase 1 relative to Baseline.
- 3. Reduction in MOS-II score at Week 4 of Phase 1 relative to Baseline.
- 4. Reduction in MOS-I score at Week 4 of Phase 1 relative to Baseline.
- 5. CGI-I score at Week 4 of Phase 1 relative to Baseline.
- 6. For subjects assigned to NTX100 in both Phases 1 and 2, reduction in IRLS Question #7 score ("How often do you get RLS symptoms?") from Baseline to Week 8.

PGI-I response at Week 4 of Phase 1 relative to Baseline will be analyzed in the same manner as the primary efficacy endpoint, except that MI methods will not be used if there are missing data.

The reduction in IRLS score at Week 4 of Phase 1 relative to Baseline will be summarized by treatment group using descriptive statistics. The null and alternative hypotheses for this endpoint are as follows:

$$\begin{array}{c} H_0\text{: } \mu_T \leq \mu_S \\ versus \\ H_1\text{: } \mu_T > \mu_S \end{array}$$

where  $\mu_T$  and  $\mu_S$  are the true means for the NTX100 treatment group and the sham control group, respectively. The null hypothesis will be tested using a one-sided, two-sample t-test at the alpha = 0.025 level.

The reductions in MOS-I and MOS-II scores at Week 4 of Phase 1 relative to Baseline will be analyzed in the same manner as the reduction in IRLS score at Week 4 of Phase 1 relative to Baseline.

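### A subject who changes medication may be removed from the whole study with no Day 28 assessment, which leaves gaps in the ITT analysis that imputation only partly covers

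*Protocol*

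**What the plan says.** Protocol 16.16 (Subject Discontinuation) opens with: "A subject may be removed from the study prior to completion for any of the following reasons". One listed reason is "Subject makes a significant change to dosage of medications known to interfere with sleep or" RLS symptoms, with sleep medications, antidepressants and sedative antihistamines as examples. Another is "Subject no longer meets inclusion criteria". The procedure that follows is: "The Investigator or research staff will complete a study exit form in the eCRF for any subject who prematurely discontinues from the study". An adverse event is recorded if it caused the discontinuation, and compensation is partial. Nothing separates stopping the device from leaving the study, and no Day 28 assessment is described for someone removed.

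The analysis side reads as follows.

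- SAP 6.1 makes ITT the primary population for all efficacy endpoints, and "subjects will be analyzed based on the treatment to which they are randomized".
- SAP 6.2 excludes from the per-protocol population anyone with a "Clinically significant change in dose or schedule of one of the following classes of medication during the study". Dropout or removal, and missing endpoint data, are separate items in the same list. Protocol 17.1.3 has the same structure.
- SAP 5.3 imputes a missing primary endpoint under missing at random, from treatment group, IRLS at Days 0 and 14, and PGI-I at Day 14.
- SAP 8.2 analyses PGI-I response like the primary endpoint, "except that MI methods will not be used if there are missing data". For the IRLS, MOS and CGI-I score endpoints it specifies t-tests and describes no imputation.
- Protocol 17.1.3 says ITT may be the primary population, yet also describes the primary-endpoint cohort as subjects with complete Day 28 data.

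**The concern.** A change in RLS or sleep medication during a four-week blinded comparison may well be a response to how symptoms are going. The documents do not say so, but it is plausible. If such a change leads to removal, the Day 28 CGI-I, PGI-I, IRLS and MOS-Sleep values are never collected, and no later analysis can recover them.

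The same event can therefore have two consequences. One site keeps the subject, who has an observed outcome in ITT and is dropped only from per protocol. Another site removes the subject, who then has an imputed primary outcome and no key secondary outcome. Neither document says which course to follow. At stake is whether the analysis labelled ITT keeps the subjects it was chosen to keep, and whether the loss is related to outcome or differs between arms.

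**Working it through.** **1. The plan's own figure.** Protocol 17.2 and SAP 3.4 inflate 112 completers for 15% dropout: 112 / (1 − 0.15) = 131.8, rounded up to 132. This reproduces. It implies 0.15 × 132 = 19.8, or about 10 of 66 per arm, without Day 28 data from all causes. No share is attributed to medication change. The inflation protects precision and does nothing about bias.

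**2. What the imputation model knows.** Its inputs are arm, IRLS at Days 0 and 14, and PGI-I at Day 14. It has no term for medication change or for the reason for removal.

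- Removed after Day 14: poor relief already visible at Day 14 is in the model. A later deterioration that prompted the change is not.
- Removed before Day 14: only arm and baseline IRLS are known, so the imputed value is close to the arm's average.

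**3. Shift in one arm.** Suppose k removed subjects are true non-responders and the model imputes response for them at rate r. The arm of 66 is overstated by k × r / 66. The documents give neither k nor r. Take k = 7 and r = 20%, 40% and 64% as assumptions:

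- 7 × 0.20 / 66 = 2.1 points
- 7 × 0.40 / 66 = 4.2 points
- 7 × 0.64 / 66 = 6.8 points

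**4. Shift in the difference.** Assume true rates of 40% active and 20% sham (20.0 points), all missing subjects non-responders, and a model that captures none of this. Each arm's estimate is then (true rate × 66) / (66 − missing).

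- 3 missing per arm: 26.4/63 − 13.2/63 = 41.9% − 21.0% = 21.0 points, a bias of about 1 point.
- 7 missing in active only: 26.4/59 − 20.0% = 24.7 points, a bias of +4.7.
- 7 missing in sham only: 40.0% − 13.2/59 = 17.6 points, a bias of −2.4.

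Treating the whole 15% dropout as this kind of loss sets an outer case: 10 missing per arm gives 26.4/56 − 13.2/56 = 23.6 points. With the same total of 20, 15 active and 5 sham missing gives 30.1 points, and 5 active and 15 sham gives 17.4. The sign depends on which arm loses more subjects.

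**5. Key secondary endpoints.** No figure is needed here. Without an imputation rule, a removed subject contributes nothing to the Week 4 PGI-I, IRLS, MOS or CGI-I score comparison, so those are completer analyses in practice.

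**The case against.** The other side has good points, and several limit the finding.

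- **Not a contradiction.** A reader might infer that the protocol and SAP conflict outright, because one removes these subjects and the other presumes their data. The text does not support that. Removal is discretionary, the per-protocol lists give removal, missing data and medication change as separate items, and SAP 5.3 plans for missing data. What stands is a gap: both courses are allowed and nothing chooses between them.
- **Inclusion criteria.** A reader might infer that subjects who improve could be removed for no longer qualifying. The severity criterion is dated, "over the week prior to study entry", and the symptom-frequency criterion likewise refers to the week before entry. Screening is scheduled only at Evaluation 1. Criteria 5 to 7 carry no date, but that anyone would re-apply them is inference. The medication trigger carries the point alone.
- **Outcome-relatedness is assumed.** The documents give no rate of medication change, no reasons and no difference by arm. Eligibility and instructions both press for stable dosing, and subjects with good relief might change doses too. This stands, and it is why direction and size are left open.
- **The primary endpoint is partly protected.** Poor relief seen at Day 14 is conditioned on. This stands for later removals and much less for earlier ones. It does not help the key secondary endpoints.
- **Post-change values mix effects.** A Day 28 score taken after a medication change reflects device and drug together. This is true, and it is a real cost of the remedy.

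The ITT definition carries an asterisk whose note is not in the public text read here, so any qualification there should be checked.

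**Conclusion.** The point holds as an unreconciled gap that should be closed. Followed as written, 16.16 can remove a subject from the study after a plausibly outcome-related event and leaves no Day 28 data. The SAP then covers the primary endpoint only partly and the other Week 4 endpoints not at all.

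The size is unknown. Under the stated assumptions, seven true non-responders removed from one arm shift it by about 2.1 to 6.8 points, and three missing per arm move the difference by about 1 point. The larger outer cases need every expected dropout to be a non-responder of this kind, invisible to the model.

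A reader might compute 7/66 = 10.6 points as the effect of seven removals. That requires all seven to flip from response to non-response, whereas the SAP fixes imputation as the counting rule, and seven has no source in the documents. Nor should the 15% dropout be read as an estimate of removals for medication change, since it covers all causes.

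**What to change.** State in Protocol 16.16 that, unless consent is withdrawn, a subject who discontinues before Day 28 still has CGI-I, PGI-I, IRLS, MOS-Sleep and adverse events collected at Evaluation 6, remotely if needed, with the reason and date of discontinuation recorded. State in the SAP that these observed values enter the ITT analysis and that medication change acts as the per-protocol exclusion already written. Reconcile 16.16, the per-protocol lists, SAP 6.1 and the complete-data sentence in Protocol 17.1.3 to match. Key secondary endpoint 6 is measured at Week 8, so this Day 28 change does not reach it.

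The cost is small: Evaluation 6 is already scheduled, and Protocol section 18 already provides for remote follow-up. The change needs a protocol revision with IRB approval under 13.5, and new consent from enrolled subjects if the IRB requires it. Some ITT values will be measured after a medication change, and the report should say so; the per-protocol analysis leaves those subjects out but does not resolve how the ITT result is read. The change must come before the data are lost. No view is taken here on medication, on device use, or on when a subject should stop treatment.

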17.1. Efficacy

17.1.1. Primary Efficacy Endpoint

The primary outcome measure will be responder rate on the CGI-I scale at Week 4 of Phase 1 relative to Baseline (study entry) and compared between the study arms.

Responder rate for the 7-point CGI-I scale will be defined as the proportion of responses of "Much

Improved" or "Very Much Improved".

17.1.2. Key Secondary Efficacy Endpoints

For all subjects:

- 1. PGI-I responder rate (defined as for CGI-I) at Week 4 of Phase 1 relative to Baseline and compared between study arms.
- 2. Mean reduction in IRLS score at Week 4 of Phase 1, relative to Baseline and compared between study arms.
- 3. Mean reduction in MOS-II (Medical Outcomes Study Sleep Problems Index I) score at Week 4 of Phase 1, relative to Baseline and compared between study arms.
- 4. Mean reduction in MOS-II (Medical Outcomes Study Sleep Problems Index II) score at Week 4 of Phase 1, relative to Baseline and compared between study arms.
- 5. Mean CGI-I score at Week 4 of Phase 1 relative to Baseline and compared between study arms.

Definition and instructions for calculation of the Medical Outcomes Study Sleep Problems Index I and II are described in [13].

17.1.3. Efficacy Analysis

A Statistical Analysis Plan (SAP) will be developed prior to breaking the blind, which will include a plan for efficacy analysis. Briefly, the Intent to Treat population may be used as the primary analysis population for all efficacy analyses, the Per Protocol population may be used as supportive, and missing data may be addressed with the use of multiple imputation. Appropriate statistical techniques will be employed to test statistical significance. If there is success on the primary endpoint, then secondary endpoints may be tested in order, according to the fixed-sequence method, until failure.

The analysis cohort for the primary efficacy endpoint are subjects who are randomized, undergo the assigned treatment, and have complete, evaluable Day 28 data. Subjects will be excluded from the Per Protocol analysis if one or more of the following occurs during or before the Phase of the study corresponding to the endpoint:

- 1. Dropout or removal from the study.
- 2. Incomplete or missing data for the endpoint.
- Clinically significant change in dose or schedule of medication that affects RLS symptoms (IC #8) or major lifestyle changes that affect RLS symptoms to a clinically significant degree (IC #9).
- 4. New medical information available after randomization indicates an exclusion criterion.
- 5. Other protocol deviation occurs that is deemed clinically significant by the investigator.

Subjects will also be excluded from the Per Protocol analysis if one or more of the following occurs during the Phase of the study corresponding to the endpoint:

- Device usage at or after bedtime on fewer than two-thirds of the nights with RLS symptoms at or after bedtime during the Phase, as reported by the subject on the Daily Questionnaire assessments.
- Missing* two or more follow-ups during the Phase (*Follow-ups completed out-ofwindow are not considered "missing")
- 8. Zero total device uses during the Phase.

17.2. Sample Size Justification

Sample size estimates are based on data from use of an earlier prototype of this investigational device in a previously approved protocol (RLS-SNS01). Based on these data and assuming a 1:1 allocation, statistical power of 85%, and 2-sided alpha of 0.05 (or 1-sided alpha of 0.025):

- For CGI-I responder rate, the sample size needed would be 42 subjects, assuming statistical treatment with a two-proportion z-test.
- For PGI-I responder rate, the sample size needed would be 42 subjects, assuming statistical treatment with a two-proportion z-test.

- For mean reduction in IRLS score, the sample size needed would be 112 subjects, assuming statistical treatment with a two-sample t-test.
- For mean reduction in CGI-I score, the sample size needed would be 36 subjects, assuming statistical treatment with a two-sample t-test.

The maximum of these is 112 subjects. Previous data with this investigational device are not available for the MOS-I or MOS-II. Based on estimates of a 15% dropout rate, 132 subjects will be enrolled in the study to yield approximately 112 completed subjects.

